11.2 Adverse Events

All AEs will be coded by the Medical Dictionary for Regulatory Activities. System organ class (SOC), high-level group term (HLGT), high-level term (HLT), preferred term (PT), and lower-level term (LLT) will be provided in the AE dataset.

Summaries will be presented for the following combinations of Treatment Sequence and Treatment Period (respective Treatment Sequences [A/B] and Treatment Periods [1/2] are given in parentheses):

- IgPro20 (A/1 and B/2)
- IgPro10 (A/2 and B/1)
- IgPro20/ Treatment Period 1 (A/1)
- IgPro20/ Treatment Period 2 (B/2)
- IgPro10/ Treatment Period 1 (B/1)
- IgPro10/ Treatment Period 2 (A/2)
- Total (A/1, A/2, B/1, and B/2)

Infusion site reactions (ISR) comprise all AEs reported within the MedDRA HLTs “Administration site reactions NEC” or “Infusion site reactions”.

Summaries of AEs created to assess the COVID-19 impact are described in Section 7.4.

Refer to Section 11.3 for the definition of Adverse Events of Special Interest (AESIs).

- An overview summary of TEAEs, including number of subjects, percentages of subjects, and the number of events by Treatment Sequence, treatment, and Treatment Period including the following:
 - Any TEAE
 - Any serious TEAE
 - TEAEs leading to interruption of IP
 - TEAEs leading to permanent discontinuation of IP
 - TEAEs leading to withdrawal from study
 - Temporally associated TEAEs
 - Treatment-emergent AESIs (Hemolysis, TEE, Acute Renal Injury)
 - Any serious treatment-emergent AESIs
 - Treatment-emergent AESIs leading to permanent discontinuation of IP
 - Treatment-emergent AESIs leading to withdrawal from study

- Related treatment-emergent AESIs
 - Treatment-emergent AESIs by Grade
 - Treatment-emergent AESIs Grade 3 and above
 - TEAEs by causality (related to IP)
 - TEAEs by severity (mild, moderate, severe)
 - TEAEs by outcome (“recovered or resolved” vs. all other outcomes combined)
 - Any ISR
 - ISRs leading to interruption of IP
 - ISRs leading to permanent discontinuation of IP
 - ISRs leading to withdrawal from study
 - ISRs by causality (related to IP)
 - ISRs by severity (mild, moderate, severe)
 - ISRs by outcome (“recovered or resolved” vs. all other outcomes combined)
- The following descriptive tables will be generated for TEAEs, including number of subjects, percentages of subjects, and the number of events:
 - TEAEs by SOC and PT
 - TEAEs by PT
 - TEAEs by SOC, PT, and maximum severity (without number of events)
 - Causally related TEAEs by SOC and PT
 - Causally related TEAEs by SOC, PT, and maximum severity (without number of events)
 - Temporally associated TEAEs by SOC, PT and maximum severity (without number of events)
 - Temporally associated TEAEs and/or causally related TEAEs by SOC, PT and maximum severity (without number of events)
 - Serious TEAEs by SOC and PT
 - Serious, causally related TEAEs by SOC and PT
 - TEAEs leading to permanent discontinuation of IP by SOC and PT
 - Treatment-emergent AESIs by Category, SOC and PT
 - Treatment-emergent AESIs by Category and PT
 - Treatment-emergent AESIs by Category, PT and maximum grade (without number of events)
 - Treatment-emergent AESIs Grade 3 and above by Category and PT
 - Serious treatment-emergent AESIs by Category and PT

-
- Related treatment-emergent AESIs by Category and PT
 - All AE summaries presented by SOC and preferred term will include a virtual SOC “Infusion Site Reactions”, i.e., all AEs reported within the MedDRA High level terms “Administration site reactions NEC”, “Infusion site reactions” or “Injection site reactions”. AEs will be presented in the virtual SOC and the regular SOC.
 - All AE summaries presented by SOC and preferred term will include a virtual SOC “Thromboembolic Events” comprising all AEs reported within the MedDRA SMQs in [Section 11.3](#). AEs will be presented in the virtual SOC and the regular SOC.

Additional summary statistics for ISR will be presented for IgPro20 Treatment Periods only (see [Table 2](#)):

- Number and percent of subjects with ISR, incl. 95% Wilson score CI
- Number and percent of subjects with ISR per week, incl. 95% Wilson score CI
An ISR will be counted for the week of the most recent infusion before the onset of the ISR.
- ISR rate per Infusion
- ISR rate per Infusion per week
- Duration of ISR
- Time to onset of ISR since start of corresponding Treatment Period
- Time to onset of ISR since start of last infusion prior to onset of AE

$$\text{ISR rate per infusion} = \frac{\text{total number of ISRs across all subjects while on IgPro20}}{\text{total number of IgPro20 Infusions across all subjects}}$$

Temporally associated TEAEs are defined as AEs with an onset between the start of the infusion and up to 72 h after the end of infusion. In case time of onset of AE is missing, the AE is considered temporally related, if the onset of the AE is between the day of the start of infusion and the day of the end of infusion + 3 days (inclusive).

The following listings will be provided:

- All Adverse Events
- Serious TEAEs
- Deaths
- Treatment-emergent AESIs

- Treatment-emergent AESIs Grade 3 or Higher
- ISRs
- TEAEs leading to permanent discontinuation of IP

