			
 • Section 9.4: Changed categories of Prior/ Concomitant Medications • Section 9.4: Summary added for concomitant medications used to treat COVID-19 associated adverse events • Section 10.1: Clarify that bootstrap method will be used to derive confidence intervals. • Section 11.1: Addition of parameters for IgPro10 • Section 11.1: Separated "Duration" into "Duration of infusion" and "Duration of Treatment" to avoid confusion • Section 11.2: Replaced "Treatment-emergent AESIs by Category, PT and grade" by "... maximum grade (without number of events)" • Section 11.2: "Injection site reaction" added to the list of HLTs to find "Infusion site reactions" • Section 11.2: Clarification of calculations for ISR • Section 11.2: Listing of TEAEs leading to permanent discontinuation of IP added • Section 11.2: Due to expected low number of events: no summary of SAE and TEAEs leading to permanent discontinuation of IP by treatment sequence • Section 12: PK analysis will be done on SAF; sensitivity analysis added for bioavailability • Section 12.2, Table 9: Reference interval for Tmax/Cmax ends at AH10/BH21 • Section 12.3: "baseline-corrected AUC " is used for bioavailability. Bioavailability will be additionally assessed by Treatment Sequence. • Section 12.3: Subject as a random effect will be dropped from the MMRM

2 List of Abbreviations

Abbreviation	Definition
ACR	American College of Rheumatology
ADaM	Analysis data model
AE	Adverse event
AMS	Aseptic meningitis syndrome
ATC	Anatomical Therapeutic Chemical
AUC	Area under the curve
AUC _{0-last}	AUC from time point zero to the last quantifiable time point
AUC _{0-tau}	AUC from time point zero to tau
CDISC	Clinical Data Interchange Standards Consortium
CI	Confidence interval
CIDP	Chronic inflammatory demyelinating polyneuropathy
CM	Concomitant medication
C _{max}	Maximum concentration
CCI	CCI
C _{trough}	Trough concentration
DRM	Data review meeting
dcSSc	Diffuse cutaneous systemic sclerosis
CCI	CCI
ECG	Electrocardiogram
eCOA	Electronic clinical outcome assessment
eCRF	Electronic case report form
EOS	End of study
EULAR	European League Against Rheumatism
FAS	Full analysis set
CCI	CCI
CCI	CCI
HIV	Human immunodeficiency index
IgA	Immunoglobulin A
IgG	Immunoglobulin G
IP	Investigational product
IRT	Interactive response technology

Abbreviation	Definition
ISR	Infusion site reaction
ITP	Immune thrombocytopenic purpura
IV	Intravenous
lcSSc	Limited cutaneous systemic sclerosis

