Treatment Sequence	The study will consist of 2 Treatment Sequences, Treatment Sequence A or Treatment Sequence B. Each subject will be randomized to 1 of the 2 Treatment Sequences.

Term	Definition
Treatment Sequence A	IgPro20 0.5 g/kg/week subcutaneous (SC) infusion in Treatment Period 1 + IgPro10 2 g/kg/4 weeks intravenous (IV) infusion in Treatment Period 2.
Treatment Sequence B	IgPro10 2 g/kg/4 weeks IV infusion in Treatment Period 1 + IgPro20 0.5 g/kg/week SC infusion in Treatment Period 2.
Treatment	Treatment will be either IgPro20 0.5 g/kg/week or IgPro10 2 g/kg/4 weeks.

3 Purpose

This statistical analysis plan (SAP) provides a detailed and complete description of the planned statistical analyses for the final analysis of the study IgPro20_2001 to support the Clinical Study Report. Mock tables, listings, and figures shells are provided in separate supporting documents.

This SAP complies with the International Conference on Harmonisation (ICH) Harmonised Tripartite Guideline Topic E9, Statistical Principles for Clinical Trials. It is based upon the following study documents:

- Case Report Form (CRF), version 10 (27 Jul 2021)
- Clinical Study Protocol, Amendment 4 (22 Feb 2021)
- Data Transfer Specification Respiratory, version 3.0 (09 May 2019)
- Data Transfer Specification eCOA, version 1.0 (05 Jun 2019)
- Data Transfer Specification ICON lab services, version 7.0 (06 May 2020)
- Data Transfer Specification ECG, version 2.0 (01 Apr 2019)
- Data Transfer Specification PK, version 1.0 (02 Sep 2020)

All decisions regarding the final analysis of the study results, as defined in this SAP document, have been made prior to Database Lock of the study data.

The PK/PD and biomarker analysis will be described and reported outside the scope of this SAP (within a separate document/report).

4 Study Design

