4.2 Objectives and Endpoints

Objectives	Endpoints
Primary	
To evaluate the safety of IgPro20 in adults with dcSSc	
 Number and percentage of subjects treatment-emergent AEs (TEAEs), serious AEs (SAEs), and AEs of special interest (AESIs) (total, by severity, by causal relationship) Number and percentage of subjects with AEs categorized as infusion site reactions (ISRs) (total, by severity, by causal relationship) Rate of ISRs per subject and per Infusion Onset and duration of ISRs Changes from baseline in vital signs and body weight, clinical laboratory tests, electrocardiogram (ECG), and pulmonary function tests (PFTs)

Objectives	Endpoints
Secondary	

To evaluate:
 
 • Relative bioavailability of IgPro20 • PK of IgPro20 • PK of IgPro10 • Safety of IgPro10 	
 • IgPro20 relative bioavailability (%F) • IgPro20 PK parameters (area under the curve [AUC]_{0-tau}, AUC_{0-last}, maximum [peak] plasma drug concentration [C_{max}], trough plasma drug concentration [C_{trough}]) • IgPro10 PK parameters (AUC_{0-tau}, AUC_{0-last}, C_{max}, C_{trough}) • The safety of IgPro10 based on: 
 ○ Number and percentage of subjects with TEAEs, SAEs, AESIs, and ISR (total, by severity, by causal relationship) ○ Changes from baseline in vital signs and body weight, clinical laboratory tests, ECG, and PFTs

CCI
 
 • CCI • • • • • • 	
 • CCI • • • • • •

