4.7 Interim Sample Size Re-estimation

Sample size re-estimation is not planned for this study.

5 Changes in the Conduct of Planned Analyses

The primary endpoint (CSP 2.1.2) requests to summarize AEs, TEAEs, AESIs, and SAEs in total and by severity and causality. In deviation to this, the summary of AEs will be restricted to TEAEs only.

In section CSP 2.2.2 “Secondary Endpoints” C_{trough} is defined as “minimum plasma drug concentration”. This is corrected to “trough plasma drug concentration”.

In section CSP 10.3.2.1 “Safety of IgPro20” 95% confidence intervals (CI) are requested for the rate of ISR per subject and per infusion. The CIs for the rate of ISR per infusion will not be calculated as the infusions are not statistically independent.

The Full Analysis Set (section CSP 10.2.1) is renamed to ITT Analysis Set, and the description was reworded for clarity. The definition of the set is not changed.

Section 10.4.2 of the CSP (Interim Analysis) states:

"An interim analysis is planned after all subjects randomized to Sequence A have finished IgPro20 treatment (Treatment Period 1). This interim analysis is planned for safety review and reporting."

The timing and purpose of the Interim Analysis has changed (see Section 4.6 of this SAP).

CSP section 10.3.3.1 requires "... subject as a random effect ..." in the model to assess relative bioavailability. This effect will not be applied.

6 Study Analysis Sets

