Adverse events associated with COVID-19, which can include a clinically significant laboratory finding like a positive test result for COVID-19, will be reported by investigators. COVID-19 associated adverse events are identified via MedDRA coding. Relevant adverse events will be identified for reporting by the broad COVID-19 standard MedDRA query (SMQ). All COVID-19 associated adverse events will be included in standard AE tables.

An overview summary table of COVID-19 associated treatment-emergent adverse events (TEAEs), including number and percentages of subjects as well as the number of events, will be provided for the following:

- Any TEAE (related/not related)
- Any serious TEAE (related/not related)
- TEAE resulting in death (related/not related)
- TEAE leading to permanent discontinuation of IP (related/not related)
- TEAE leading to interruption of IP (related/not related)
- TEAE leading to withdrawal from study (related/not related)
- TEAE by severity (mild, moderate, severe, missing)

A listing showing all COVID-19 associated adverse events will be provided.

A descriptive table will be generated for all COVID-19 associated TEAEs by PT, including number of subjects, percentages of subjects, and the number of events.

COVID-19 Vaccinations

Sites will be prompted to inquire whether a subject has received a COVID-19 vaccination and to record each dose of the vaccine on the concomitant medications form along with the exact date of administration and manufacturer of the vaccine. Standardised Drug Grouping (SDG) from WHO Drug Dictionary will be utilized to identify COVID-19 vaccines using the narrow SDG 'Vaccines for COVID-19'.

For subjects receiving COVID-19 vaccination during the study all treatment-emergent adverse events occurring within 7 days of COVID-10 vaccination will be summarized by System Organ Class and preferred term.

Visit Modality, Missed Visits and Missing Assessments

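### SAP 11.2 gives two HLT lists for infusion site reactions; read literally, an event coded only to the third HLT is left out of the primary ISR outputs but shown as an infusion site reaction in the SOC/PT tables

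*SAP*

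**What the plan says.** SAP 11.2 defines the term once: "Infusion site reactions (ISR) comprise all AEs reported within the MedDRA HLTs “Administration site reactions NEC” or “Infusion site reactions". Further on in 11.2, every summary by SOC and preferred term is to carry a virtual SOC named for infusion site reactions. Its content is "all AEs reported within the MedDRA High level terms “Administration site reactions NEC”, “Infusion site reactions” or “Injection site reactions". Both sentences are current text.

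The outputs that use the label ISR are:

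- seven overview rows in 11.2 (any ISR; leading to interruption, to permanent discontinuation, to withdrawal; by causality, severity and outcome);
- "Number and percent of subjects with ISR, incl. 95% Wilson score CI", overall and by week;
- the rate per infusion, overall and by week;
- duration and two onset measures;
- the ISR listing.

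SAP 4.2 places ISRs in the primary endpoint: subjects with ISRs, onset and duration, and "Rate of ISRs per subject and per Infusion". The protocol (2.1.2) does the same but gives no HLT-level definition. On the per-infusion rate, SAP 5 adds: "The CIs for the rate of ISR per infusion will not be calculated as the infusions are not statistically independent".

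The SAP's modification history records, for Section 11.2, that the injection-site term was "added to the list of HLTs to find" infusion site reactions.

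**The concern.** One section gives two answers to the question of what an infusion site reaction is. The two-HLT sentence is the only definition of the label ISR, so a programmer who follows the text applies it to every output with that label. The virtual SOC has its own, longer list. An event coded only to *Injection site reactions* would then be absent from the primary ISR outputs and present under Infusion Site Reactions in the SOC/PT tables of the same report.

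Two things are at stake. Subject and event counts for what looks like one concept could differ between tables without explanation. Any difference also runs one way: the two-HLT set is contained in the three-HLT set, so the primary ISR counts, percentages and rate can match the wider definition or fall below it, but never exceed it. In a study whose primary objective is the safety of a subcutaneous product in patients with diseased skin, that choice should be settled before the coded events are reviewed.

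**Working it through.** **The plan's own figure.** Protocol 10.1 and SAP 4.5 give 20 subjects x 28 infusions = 560. The 28 follows from the SAP glossary: 14 weekly infusions x 2 sessions. With the Wilson formula and n = 560, the chance of a half-width of at most 0.0261 at a rate of 0.1 is 0.821. At a rate of 0.5 the half-width is 0.0413, within the stated 0.0414. These figures reproduce and do not depend on the HLT list, so no design figure changes.

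**The two lists side by side.**

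| HLT | ISR definition | Virtual SOC |
|---|---|---|
| Administration site reactions NEC | yes | yes |
| Infusion site reactions | yes | yes |
| Injection site reactions | no | yes |

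They differ by exactly one term. Nothing else in the SAP or protocol reconciles them.

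**Effect of one event coded only to the third HLT.**

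- Overall rate per infusion: 1/560 = 0.0018. At the expected rate of 0.1 there are 0.1 x 560 = 56 ISRs, and 1/56 = 1.8%.
- Rate for a single week: 20 subjects x 2 infusions = 40, so 1/40 = 0.025.
- Subject percentage, if it is that subject's only ISR: 1/20 = 5.0 points, or 1/26 = 3.8 points if all 26 planned enrollees are treated. If the subject has another ISR that counts, the change is 0.

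**Range for the unknown share.** The documents do not say what share of ISRs would code only to the third HLT. With an assumed share s and a three-HLT rate of 0.1, the two-HLT rate is 0.1 x (1 - s):

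| Assumed share s | Expected two-HLT count | Two-HLT rate |
|---|---|---|
| 0% | 56 | 0.100 |
| 10% | 50.4 | 0.090 |
| 25% | 42 | 0.075 |
| 50% | 28 | 0.050 |

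**Subject percentages with Wilson 95% intervals (assumed counts, one added subject).**

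- 5/20 = 25.0% (11.2 to 46.9) becomes 6/20 = 30.0% (14.5 to 51.9).
- 10/20 = 50.0% (29.9 to 70.1) becomes 11/20 = 55.0% (34.2 to 74.2).

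The per-infusion rate carries no interval under SAP 5, so its shift is not set against a precision figure.

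**Minor check, SAP 8.2.3.** Onset since the last infusion and AE duration are both labelled in minutes. The onset formula divides the date-time difference by 60; the duration formula does not. If date-times are held in seconds, as the onset divisor implies, a 2-hour event is 7,200 s, and 7,200/60 = 120 minutes.

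**The case against.** The strongest reply is that one sentence was simply not updated. The modification history points to the three-HLT list, and SAP 3 says of the outputs: "Mock tables, listings, and figures shells are provided in separate supporting documents". Those shells are not available here and may already use one list. No document suggests that any event will code only to the third HLT. One subject's shift of 5.0 points is also small against intervals 35.7 points wide (46.9 - 11.2) or 40.2 points wide (70.1 - 29.9). All of this stands and limits the weight of the point. It does not remove the contradiction, because the SAP presents itself as the full description of the analysis and its defining sentence is the one that names two HLTs.

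A reader might infer more than the documents support:

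- *That infusion site reactions would go unreported.* They would not. Such an event stays in the TEAE counts, in its regular SOC and the virtual SOC, and in the listing of all adverse events.
- *That the per-infusion rate would visibly clash with the SOC/PT tables.* Those tables give subjects, percentages and event counts, not rates. Only subject and event counts can be seen to disagree; the weekly rate, onset and duration have no counterpart there.
- *That ISRs without clock times disappear untraced.* SAP 8.2.3 does set their duration and onset since last infusion to missing. But SAP 7 requires the number of observations in every continuous summary, and the overview gives ISR event counts, so the gap can largely be read off. No extra count is needed.
- *That durations will be wrong by a factor of 60.* The unit is stated as minutes, so the intention is clear, and a divisor lost in typesetting cannot be excluded.

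A further fair objection is that the wider list may pick up reactions to other injections. SAP 7.4 foresees these: "For subjects receiving COVID-19 vaccination during the study all treatment-emergent adverse events occurring within 7 days". The documents do not show which HLT such a reaction would fall under, so the risk cannot be confined to the third. The fix has to cover all three.

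**Conclusion.** The point holds as an inconsistency in the definition behind part of the primary endpoint, and it should be corrected before database lock. It rests on a literal reading of two current sentences in SAP 11.2. The modification history serves only as evidence of which list was intended.

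The actual size is unknown and is zero if no event codes only to *Injection site reactions*. The per-event and per-subject shifts shown assume the planned 20 subjects and 560 infusions. The direction is certain: the literal definition cannot give higher ISR figures than the three-HLT list. No hypothesis test depends on it (SAP 7.3), so the consequence is confined to the reported safety estimates and their agreement across tables. The documents do not support a claim that the ISR results will be materially biased.

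**What to change.** Before database lock:

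1. State one ISR definition in SAP 11.2, the three-HLT list, and refer to it for the overview rows, subject percentages with Wilson intervals, overall and weekly rates, onset, duration, the ISR listing and the virtual SOC. Check that the table shells use the same list.
2. If the data review meeting excludes a reaction attributed to an injection other than study product, under any of the three HLTs, apply the exclusion identically in all ISR outputs and the virtual SOC, and list the excluded events. They remain in the general adverse event outputs. Without this rule the mismatch could return by another route.
3. Minor: make the AE duration formula in SAP 8.2.3 agree with its stated unit of minutes, as the onset formula does.

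The cost is a short SAP edit and a small programming change. No new data are needed. The wider list may bring in reactions to other injections, which step 2 handles.

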2.1.2 Primary Endpoints

The primary endpoint of the study is the safety of IgPro20 based on:

Safety Endpoints	Summary Measure
AEs, including any AEs, treatment-emergent adverse events (TEAEs), serious adverse events (SAEs), and adverse events of special interest (AESIs)	
AEs measured by treatment, treatment sequence, combination of treatment, and treatment period (Period 1, Week 16; Period 2, Week 32; combination of treatment, Week 32):
 
 Number and percentage of subjects with AEs, TEAEs, SAEs, and AESIs (total, severity, causality, and outcome) Number and percentage of subjects with AEs categorized as ISRs (total, severity, causality and outcome) Rate of ISRs per subject and per infusion Onset and duration of ISRs
Change in other clinical tests	
Changes from baseline as measured by treatment, treatment sequence, combination of treatment and treatment period:
 
 Vital signs Body weight Clinical laboratory tests Electrocardiogram (ECG) Pulmonary function tests (PFTs)

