10.3.2 Analyses of Primary Endpoints

10.3.2.1 Safety of IgPro20

Safety data collected while subjects are treated with IgPro20 will be summarized by treatment sequence. All AEs will be coded by the Medical Dictionary for Regulatory Activities in System Organ Class and Preferred Term. Treatment-emergent adverse events, defined as AEs reported at or after the start of the first infusion in the study, will be summarized in number and percentages by treatment sequence. Summaries of TEAEs by

severity, causal relationship, seriousness, and leading to interruption and / or withdrawal will be provided.

Infusion site reactions will also be summarized separately following the analyses for all TEAEs. Additional summary statistics including 95% CIs will be presented for rate of ISRs per subject and per infusion. Descriptive statistics of time to onset and duration of ISRs will be presented. Detailed information about ISRs related to infusion sites will be provided.

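### SAP 11.2 gives no ISR rate per subject although SAP 4.2 keeps it as a primary endpoint and SAP 5 declares no change; neither count-based ISR rate has an interval, yet SAP 4.5 still cites one

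*SAP*

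**What the plan says.** Protocol 2.1.2 lists the number and percentage of subjects with ISRs as one primary summary measure and, as a separate bullet, "Rate of ISRs per subject and per infusion". Protocol 10.3.2.1 adds: "Additional summary statistics including 95% CIs will be presented for rate of ISRs per subject and per infusion".

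SAP 4.2 keeps both bullets; the second reads "Rate of ISRs per subject and per Infusion". SAP Section 5, which records changes from the protocol, restates the request for intervals on both rates and withdraws one of them: "The CIs for the rate of ISR per infusion will not be calculated as the infusions are not statistically independent". It says nothing about the rate per subject.

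SAP 11.2 then sets out the additional ISR statistics for the IgPro20 periods. Two carry intervals: "Number and percent of subjects with ISR, incl. 95% Wilson score CI" and "Number and percent of subjects with ISR per week, incl. 95% Wilson score CI". The ISR rate per infusion, overall and by week, is a point estimate, defined as total ISRs divided by total IgPro20 infusions across all subjects. Duration and time to onset complete the list. No ISR count or rate per subject appears.

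SAP 4.5 repeats the protocol's precision statement: 20 subjects, 28 infusions each and 560 in all. The Wilson 95% half-width for the rate per infusion is at most 0.0261 with 80% probability if the rate is 0.1, and at most 0.0414 if it is 0.5.

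**The concern.** A measure that the SAP still names as primary has no defined calculation, and the interval promised for it has gone without being recorded as a change. The interval for the companion rate is withdrawn openly, but the precision statement for that interval remains in the same document.

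ISR burden under repeated subcutaneous dosing in skin affected by systemic sclerosis is central to the primary objective. A percentage of subjects does not separate someone with one reaction from someone with many, and a pooled rate without an interval does not show how precisely 20 subjects estimate it. The analysis of the per-subject rate is also left to be settled after the SAP is final.

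**Working it through.** **1. Endpoints against analyses**

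| Measure | Protocol 2.1.2 / SAP 4.2 | 95% CI promised in Protocol 10.3.2.1 | SAP 11.2 | Change declared in SAP 5 |
|---|---|---|---|---|
| Percentage of subjects with an ISR | listed | not in that sentence | given, Wilson CI; also per week | none bearing on the CI |
| ISR rate per infusion | listed | yes | given, no CI | yes, CI withdrawn |
| ISR rate per subject | listed | yes | absent | none |

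**2. The plan's precision figures**

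Inputs (Protocol 10.1, SAP 4.5): n = 20 × 28 = 560; rate p = 0.1 or 0.5. Wilson half-width:

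h = z·√[p(1−p)/n + z²/(4n²)] / (1 + z²/n), z = 1.96,

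evaluated over the exact Binomial(560, p) distribution.

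- p = 0.1: the 80th percentile of h is 0.0260, and P(h ≤ 0.0261) = 0.82. The value of h at exactly 10% is 0.0249.
- p = 0.5: the largest h is 0.0413, so ≤ 0.0414 is true.

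Both figures reproduce. Both treat the 560 infusions as independent, which SAP Section 5 says they are not.

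**3. Precision when infusions cluster within subjects**

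The documents give no within-subject correlation, so these ICC values are assumptions. With at most one ISR per infusion, the design effect is 1 + 27·ICC and the approximate expected half-width is

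1.96·√[p(1−p)/560 × (1 + 27·ICC)].

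For p = 0.1:

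| ICC (assumed) | Design effect | Half-width, formula above | Wilson with effective n |
|---|---|---|---|
| 0 | 1.00 | 0.0248 | 0.0249 |
| 0.05 | 2.35 | 0.0381 | 0.0383 |
| 0.1 | 3.70 | 0.0478 | 0.0482 |
| 0.3 | 9.10 | 0.0750 | 0.0764 |

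For p = 0.5, the effective-n Wilson half-widths at the same ICCs are 0.041, 0.063, 0.079 and 0.121. The like-for-like comparator for the p = 0.1 column is 0.025, the expected half-width under independence. The plan's 0.0261 is an 80%-probability bound.

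**4. The missing per-subject statistic is estimable**

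Mean ISRs per subject = 28p. Variance per subject = 28p(1−p)(1 + 27·ICC). With 20 subjects and t on 19 degrees of freedom (2.093), half-width = 2.093·√(variance/20). At p = 0.1 the mean is 2.8, with half-width 0.74, 1.14, 1.43 and 2.24 at ICC 0, 0.05, 0.1 and 0.3.

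Subjects are the independent units, so non-independence of infusions does not prevent this interval. It rules out only the simple Wilson interval on 560 infusions.

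**The case against.** The strongest reply is that the sponsor meant 'rate per subject' as the proportion of subjects with an ISR. Section 5 withdraws only the per-infusion interval, 11.2 puts Wilson intervals on subject proportions, and the protocol itself applies Wilson, a method for proportions, to an ISR rate. On that reading nothing was dropped. This cannot be excluded: neither document defines the term, and the table shells are in separate documents. But the rate bullet would then duplicate the percentage bullet beside it in both documents, and 11.2 defines its other ISR rate as a ratio of counts. If the proportion was meant, the SAP should say so, so a text change is due either way.

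Two stronger readings are tempting, and the documents do not support them.

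- A reader might infer that the trial will hold no result on ISRs per subject. The overview table in SAP 11.2 gives subjects and number of events for any ISR, and all ISRs are listed, so a crude mean can be worked out. What is missing is a defined statistic, its spread and its interval.
- A reader might infer that the percentages are useless because nearly every subject will have an ISR. At rate 0.1 over 28 independent infusions, 1 − 0.9²⁸ = 95% would. That assumes independence; under a beta-binomial model the figure is 84%, 74% and 48% at ICC 0.05, 0.1 and 0.3. It cannot be combined with the widened intervals, which assume clustering. The SAP also gives weekly percentages with intervals. At two infusions a week and independence these are about 1 − 0.9² = 19% at rate 0.1 and 1 − 0.5² = 75% at rate 0.5, which are not at a ceiling.

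It is also fair that the per-infusion interval was withdrawn openly and for a sound reason, and that the sample size rests mainly on feasibility. With about 20 clusters, the choice of a clustered method is a matter of judgement.

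**Conclusion.** The point holds as an undeclared omission and an internal inconsistency. SAP 4.2 names a per-subject ISR rate as primary, 11.2 gives none, and Section 5 does not record the difference. Neither count-based ISR rate has an interval; the percentages of subjects do. SAP 4.5 states a precision for an interval that Section 5 says will not be calculated. The undeclared omission and the stranded precision statement are wrong as written. Adding a clustered interval is a cheap improvement.

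On size, the cited half-widths are arithmetically right under independence. At rate 0.1 and assumed ICCs of 0.05 to 0.3, the expected half-width is about 1.5 to 3 times the independent value (0.038/0.025 to 0.075/0.025). This rests on 20 subjects with 28 infusions each, equal exposure, and at most one ISR per infusion. The last is a simplification: 11.2 counts all ISRs, and Protocol 5.1.3 allows up to four infusion sites at once. The documents do not establish that the sponsor deliberately replaced the per-subject rate with the percentage.

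**What to change.** - **SAP 11.2:** add ISRs per subject for the IgPro20 periods, both as a count and as the count divided by that subject's IgPro20 infusions, with mean, median and a subject-level 95% CI.
- **SAP 11.2:** give the pooled rate per infusion a 95% CI clustered by subject, for example by a subject-level bootstrap. Poisson GEE with robust variance and log infusions as offset is an alternative.
- **SAP 5:** revise the entry on the per-infusion interval to match. If the sponsor intends 'rate per subject' to mean the proportion of subjects, or chooses not to report a per-subject rate, record that here and align 4.2.
- **SAP 4.5:** note that the half-widths 0.0261 and 0.0414 assume independent infusions and will not be met under clustering of the kind illustrated.

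No new data are needed. The cost is a little programming and a reported interval wider than the one cited in 4.5.
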